### TABLE OF CHANGES

SAP version 2.0	SAP version 3.0	Reason for Change
3.4 Other Endpoint: Echocardiographic parameters	Updated the wording to be exactly matched with protocol [REDACTED]	[REDACTED]
4. Analysis Population	Added "Rev [REDACTED] and after" to be more clear for analysis population.	[REDACTED]
4.3 Per-protocol Population	Change protocol population to be consistent [REDACTED]	[REDACTED]
7.1 Patient Enrollment and Accountability	Removed wording to be consistent with TMTT standard table shells.	[REDACTED] [REDACTED]
8.4.1 Echocardiographic parameters	Updated the wording to be exactly matched with protocol Rev [REDACTED]	[REDACTED]
8.4.2 Clinical parameters	Change SF-36 to SF-12	Corrected error.
8.4.3 Additional Safety Analysis	Removed "DMC adjudicated AEs and SAEs"	Per safety adjudication rule update, only MAE and study endpoints will be CEC

	Revision Date: April 1, 2019		Rev	3.0	For Use Only by Affiliates of Edwards Lifesciences	Page 3 of 18
	Title	Statistical Analysis Plan for FORMA EFS				

		adjudicated. AE and SAE will no longer require CEC adjudication.
9. Changes From Protocol Specified Analyses	Updated per Rev ■	Per protocol Rev ■

Final

	Revision Date: April 1, 2019	Rev	3.0	For Use Only by Affiliates of Edwards Lifesciences	Page 4 of 18
	Title	Statistical Analysis Plan for FORMA EFS			

## GLOSSARY OF TERMS:

ABBREVIATION	DEFINITION OR DESCRIPTION
AKI	Acute Kidney Injury
AT	As-treated population
BMI	Body Mass Index
BNP	Brain Natriuretic Peptide
CI	Confidence Interval
CIP	Clinical Investigational Plan
DMC	Data Monitoring Committee
ECG	Electrocardiogram
eCRF	electronic Case Report Form
EROA	Effective Regurgitant Orifice Area
HF	Heart Failure
ITT	Intent-to-treat
KCCQ	Kansas City Cardiomyopathy Questionnaire
KCCQOS	KCCQ Overall Summary Score
KM	The Kaplan-Meier Method
Max	Maximum
Min	Minimum
MCS	Mechanical Circulatory Support
NYHA	New York Heart Association
PCS-12	Physical Health Summary score
PE	Pericardial Effusion
PP	Per protocol
PPM	Permanent Pacemaker
QoL	Quality of Life
SAP	Statistical Analysis Plan
SAE	Serious Adverse Event
SD	Standard deviation
SF-12	Medical Outcomes Study 12-Item Short-Form Health Survey
SVC	Superior Vena Cava
TV	Tricuspid Valve
TR	Tricuspid Regurgitation
VCW	Vena Contracta Width

 Edwards	Revision Date: April 1, 2019		Rev	3.0	For Use Only by Affiliates of Edwards Lifesciences	Page 7 of 18
	Title	Statistical Analysis Plan for FORMA EFS				

## 1. INTRODUCTION

The statistical analysis plan (SAP) specifies the statistical methods to be implemented for the analysis of data collected within the scope of Edwards Lifesciences Protocol, study #2014-04, Early Feasibility Study of the Edwards FORMA Tricuspid Transcatheter Repair System, and provides detailed instructions as to how each analysis will be performed. This SAP v3.0 is based on Protocol Rev M.

Results obtained from the analyses specified in the final approved version of the SAP will become the basis of the clinical study report (CSR) for this study. Any deviations from the final approved version of the SAP must be substantiated by sound statistical reasoning and documented in the CSR.

Final

 Edwards	Revision Date: April 1, 2019		Rev	3.0	For Use Only by Affiliates of Edwards Lifesciences	Page 8 of 18
	Title	Statistical Analysis Plan for FORMA EFS				

## 2. STUDY DESIGN

### 2.1 Study Objectives

The objectives of this early feasibility study are to:

- Evaluate the safety and function of the Edwards FORMA System
- Provide guidance for future clinical study designs utilizing the Edwards FORMA System
- Provide guidance for future FORMA System development efforts.

### 2.2 Overall Study Design and Plan

This is a multi-site, prospective, early feasibility study. 60 patients will be enrolled in the study. All enrolled study patients will be assessed for clinical follow-up at the following intervals: 1 month, 6 months, 1 year and annually for 3 years post implant procedure.

### 2.3 Sample Size Consideration

This clinical study will enroll 60 patients. This sample size was established based on typical sample size for early feasibility studies and no statistical justification was utilized.

### 2.4 Patient Enrollment

All patients enrolled under Revision [REDACTED] and later of the Clinical Protocol, will be consented, treated and followed according to the requirements described in protocol Revision [REDACTED] and later. Patients enrolled under previous versions of the Clinical Protocol [REDACTED] will not be required to re-consent under Revision [REDACTED], those patients will be followed according to the requirements of the protocol version to which they were consented.

 Edwards	Revision Date: April 1, 2019		Rev	3.0	For Use Only by Affiliates of Edwards Lifesciences	Page 9 of 18
	Title	Statistical Analysis Plan for FORMA EFS				

### 3. STUDY ENDPOINTS

#### 3.1 Safety Endpoints

Composite of major adverse events (MAE) defined as cardiovascular mortality, myocardial infarction, new need for renal replacement therapy, severe bleeding, re-intervention and major access site and vascular complications at 30 days.

#### 3.2. Performance Endpoints

##### 3.2.1 Device success

Device is deployed as intended and the delivery system is successfully retrieved as intended at the time of the patient's exit from the cardiac catheterization laboratory.

##### 3.2.2 Procedural success

Device success with evidence of tricuspid regurgitation (TR) reduction as evidenced by a relative reduction in EROA of  $\geq 30\%$  from baseline to discharge and without the need for a surgical or percutaneous intervention prior to hospital discharge.

##### 3.2.3 Clinical success

Procedural success without MAEs at 30 days. (MAEs: cardiovascular mortality, myocardial infarction, new need for renal replacement therapy, severe bleeding, re-intervention and major access site and vascular complications).

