5.1.2.3 Clinical Success

Procedural success without MAEs at 30 days. (MAEs: cardiovascular mortality, myocardial infarction, new need for renal replacement therapy, severe bleeding, re-intervention and major access site and vascular complications)

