| 
Death (MVARC)
 | 
Cardiovascular (CV) Death
 
The primary cause of CV death will be categorized using the following choices:
 
 ○ Arrhythmia and/or conduction system disturbance ○ Cardiovascular infection and sepsis (e.g. Endocarditis) ○ Device failure ○ Heart failure ○ Major bleeding ○ Myocardial Infarction ○ Stroke ○ Sudden, unexpected death / unknown ○ Tamponade ○ Thromboembolism ○ Other CV cause 
If death was due to a heart failure, it will be sub classified into:
 
 ○ LV dysfunction ○ RV dysfunction ○ Biventricular dysfunction 
Non-Cardiovascular (CV) Death
 
A diagnosis of non-CV death requires the primary cause to be clearly related to another condition due primarily to an identifiable non-CV cause or etiology. Specific diagnoses may include respiratory failure, pneumonia, trauma, suicide, or any other non-cardiovascular defined causes (e.g., liver disease, malignancies etc.) not included in the previous categories.
 
Primary cause of non-CV death
 
The primary cause of non-CV death will be categorized using the following choices:
 
 ○ Adverse drug reaction or overdose ○ Cancer ○ Gastrointestinal |
|-----------------------------|--|

| | |
|--|--|
| | 
 ○ Liver failure ○ Non-cardiovascular infection and sepsis (e.g. pneumonia) ○ Pancreatic ○ Renal failure ○ Respiratory Failure ○ Trauma ○ Other non-CV cause |
| Device Deficiency (ISO 14155:2011) | An inadequacy of a medical device with respects to its identity, quality, durability, reliability, safety or performance. Device deficiencies include malfunctions, use errors and inadequate labeling. |
| Device Fracture | Break or other structural defect in anchor, railing, or spacer with or without embolization |
| Device Malfunction | Device malfunction is defined in as a failure of an investigational medical device to perform in accordance with its intended purpose when used in accordance with the Instructions for Use. See “Device Deficiency” |
| Device Success | Device is deployed as intended and the delivery system is successfully retrieved as intended at the time of the patient’s exit from the cardiac catheterization laboratory. |
| eGFR | Estimated glomerular filtration rate |

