| MAE | Major adverse event defined as cardiovascular mortality, myocardial infarction, new need for renal replacement therapy, severe bleeding, re-intervention and major access site and vascular complications |
| Malfunction | Refer to ISO 14155 definition |
| Mortality | See "Death" |

Final

| | |
|---|---|
| 
Myocardial Infarction (MVARC)
 | 
 ○ Periprocedural MI (≤48 hours after index procedure procedure)*†: 
A. In patients with normal baseline CK-MB (or cTn):
 
 ○ The peak CK-MB measured within 48 h of the procedure rises to ≥10x the local laboratory ULN (Upper Limit of Normal) PLUS new ST-segment elevation or depression of ≥1 mm in ≥2 contiguous leads (measured 80 ms after the J-point) ○ The peak CK-MB measured within 48 h of the procedure rises to ≥5x ULN with new pathological Q waves in ≥2 contiguous leads or new persistent LBBB ○ In the absence of CK-MB measurements and a normal baseline cTn, a cTn (I or T) level measured within 48 h of the PCI rises to ≥70x the local laboratory ULN PLUS new ST-segment elevation or depression of ≥1 mm in ≥2 contiguous leads (measured 80 ms after the J-point) ○ The peak CK-MB measured within 48 h of the procedure rises to ≥35x ULN with new pathological Q waves in ≥2 contiguous leads or new persistent LBBB. 
B. In patients with elevated baseline CK-MB (or cTn): The CK-MB (or cTn) rises by an absolute increment equal to those levels recommended above from the most recent pre-procedure level plus, new ECG changes as described.
 
 ○ Spontaneous MI (>48 hours after index procedure procedure): 
Detection of rise and/or fall of cardiac biomarkers (preferably cTn) with at least 1 value above the 99th percentile URL (or ULN in the absence of URL) together with at least 1 of the following:
 
  Symptoms of ischemia  ECG changes indicative of new ischemia (new ST-segment or T-wave changes or new LBBB) or new pathological Q waves in ≥2 contiguous leads  Imaging evidence of a new loss of viable myocardium or new wall motion abnormality |
|---|---|

| | |
|--|---|

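### Clinical success at 30 days does not require survival, so a patient with procedural success who dies of an identified non-cardiovascular cause, with no other MAE, meets the written definition

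*SAP*

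**What the plan says.** The performance endpoints are nested.

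- **Device success** (SAP 3.2.1, Protocol 5.1.2.1) is judged on leaving the catheterization laboratory: "Device is deployed as intended and the delivery system is successfully retrieved as intended at the time of the patient's exit".
- **Procedural success** (SAP 3.2.2, Protocol 5.1.2.2) adds a "relative reduction in EROA of" at least 30% from baseline to discharge, "without the need for a surgical or percutaneous intervention prior to hospital discharge".
- **Clinical success** (SAP 3.2.3) is "Procedural success without MAEs at 30 days. (MAEs: cardiovascular mortality, myocardial infarction" and four further event types, none of which is a death. Protocol 5.1.2.3 has the same definition.

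Protocol Section 18 gives the same MAE list: "Major adverse event defined as cardiovascular mortality, myocardial infarction, new need for renal replacement therapy, severe bleeding", then re-intervention and the access site and vascular complications.

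Section 18 also separates cardiovascular from non-cardiovascular death. Sudden, unexpected or unknown deaths are cardiovascular. For the other category, "A diagnosis of non-CV death requires the primary cause to be clearly related to another condition". The listed non-cardiovascular causes include liver, renal and respiratory failure, non-cardiovascular infection and gastrointestinal causes.

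SAP 8.2 assesses clinical success in the as-treated cohort at the 1-month interval. SAP 6.1 takes patients with missing data out of the denominator, and SAP 6.2 rules out imputation. SAP 3.3.1 opens FDA Device Success, at 1 month and later visits, with a requirement that the patient be alive.

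**The concern.** An endpoint called clinical success at 30 days should not be met by a patient who is dead at day 30. No sentence in either document says how a non-cardiovascular death by day 30 enters the numerator or the denominator, and both available treatments raise the reported rate.

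The result for such a patient also turns on cause of death. Two patients who die on the same day after the same procedure can be classified in opposite ways. One report could show the same patient as a clinical success and as an FDA device failure at the same visit. The study is meant to guide later designs (Protocol Section 4, SAP 2.1), so a definition with this gap could be carried forward.

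**Working it through.** **Step 1. Walk one patient through the definition.** Take an as-treated patient whose device is placed as intended, whose discharge EROA is at least 30% below baseline, who has no intervention before discharge, and who dies of respiratory failure on day 15 with no other event.

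| Requirement | Source | Result |
|---|---|---|
| Device success | SAP 3.2.1 | met |
| EROA reduction at discharge | SAP 3.2.2 | met |
| No intervention before discharge | SAP 3.2.2 | met |
| No cardiovascular death | SAP 3.2.3, Protocol 18 | met (death is non-cardiovascular) |
| None of the other five MAE types | SAP 3.2.3 | met |
| **Clinical success** | SAP 3.2.3 | **met** |
| **FDA Device Success, 1 month** | SAP 3.3.1 | **not met** |

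**Step 2. The alternative treatment.** If the absent 1-month assessment is treated as missing, SAP 6.1 and 6.2 drop the patient. This is less direct than step 1, because MAE status up to death is known. It does not make the death a failure either.

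**Step 3. Size.** The plan has no figure to reproduce: SAP 2.3 says that the sample of 60 has no statistical justification, and no success rate or 30-day death rate is given. The counts below are assumptions. Let n be the as-treated number, S the patients who are alive at day 30 and meet the definition, and d the patients who meet it as written but died of a non-cardiovascular cause by day 30.

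- Death as failure: S/n
- Death counted as success: (S + d)/n, an excess of d/n
- Death dropped: S/(n − d), an excess of S·d/[n(n − d)]

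One death counted as success adds 1/60 = 1.7 points, or 1/30 = 3.3 points in each of the two subgroups planned in SAP 4 and 8.4.4.

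The table assumes that all enrolled patients are as-treated and that 70% meet the definition as written:

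| n | d | Counted as success | Dropped | Failure |
|---|---|---|---|---|
| 60 | 1 | 42/60 = 70.0% | 41/59 = 69.5% | 41/60 = 68.3% |
| 60 | 2 | 42/60 = 70.0% | 40/58 = 69.0% | 40/60 = 66.7% |
| 60 | 3 | 42/60 = 70.0% | 39/57 = 68.4% | 39/60 = 65.0% |
| 30 | 1 | 21/30 = 70.0% | 20/29 = 69.0% | 20/30 = 66.7% |
| 30 | 3 | 21/30 = 70.0% | 18/27 = 66.7% | 18/30 = 60.0% |

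For scale, the exact 95% interval (Clopper-Pearson, the method in SAP 6.1) is 56.8% to 81.2% for 42/60 and 51.6% to 76.9% for 39/60.

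**The case against.** The case for leaving the text alone has four parts.

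**The gap is narrow.** This stands. The patient must have procedural success, an identified non-cardiovascular cause of death and no earlier MAE. Severe bleeding or new renal replacement therapy on the way to death already makes the patient a failure, and unexplained deaths are cardiovascular by definition. The exclusion criteria also remove patients with low eGFR or dialysis, significant frailty, cachexia or life expectancy under 12 months. A reader might infer that a patient who dies of a non-cardiovascular cause can never be a failure. The documents do not support that.

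**Such deaths are visible elsewhere.** This stands in part. SAP 8.3 reports each component of the FDA endpoints, including survival, and SAP 8.4.3 summarises early adverse events and lists all of them. That shows the deaths but does not correct the clinical success percentage. SAP 3.3 presents the FDA endpoints as additional, so different results under the two sets are not a contradiction in themselves.

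**A death before the discharge echo could already be a failure.** Procedural success asks for evidence of TR reduction, and a patient without a discharge EROA has none. That reading is available. SAP 6.1 and 6.2 point the other way, and nothing settles which applies. It would be too strong to say that the plan necessarily drops these patients.

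**Nothing rests on this percentage.** Largely right. The study is descriptive, with no hypothesis test or performance goal. A reader might take clinical success to be the main endpoint, but it is one of three performance endpoints and the documents do not rank them. MAE data are committee-adjudicated (SAP 8.1, 8.2), which improves the cause-of-death classification but leaves the endpoint dependent on it.

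**Conclusion.** The point holds in a limited form. As written, clinical success can be met by a patient who died of an identified non-cardiovascular cause by day 30, or that patient can be dropped. Neither treatment lowers the rate, so the error is always favourable. Counted as success, each such death adds 1.7 points at n = 60 and 3.3 points at n = 30. Dropped, under the 70% assumption above, one death adds about 1.2 and 2.3 points. These sizes rest on an assumed number of deaths, an assumed success rate and full as-treated numbers. One death moves the rate far less than the width of its interval (about 24 points at 42/60). The effect is on a reported percentage, not on an error rate or a formal decision. It is worth correcting because the classification is wrong for the patient concerned and the remedy is small.

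**What to change.** - **SAP 3.2.3 and 8.2:** state that clinical success requires procedural success, survival to day 30 and no MAE through day 30. Death from any cause by day 30 is a failure and stays in the denominator. Take survival from the reported deaths, not from attendance at a visit whose window runs from day 23 to day 37 (SAP 5.2).
- **SAP 3.2.2:** state that death before discharge is a procedural failure, not a missing EROA.
- **SAP 8.1:** show 30-day all-cause mortality beside the cardiovascular mortality component.
- **SAP 9:** record the convention as a change from the protocol text, and apply it to patients enrolled before Rev L and to those enrolled under Rev L and after.
- **Protocol 5.1.2.3:** align the wording at the next amendment.

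The MAE definition stays as it is. No new data are needed, because Protocol 12.4.1 already requires every death to be reported within one business day. The costs are a SAP revision now, a protocol wording change that goes through the approvals in Protocol 16.5, and a success rate that may be slightly lower, since a death unrelated to the device would also count as a failure. FDA Device Success already treats such a death that way.

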#### 3.3 FDA Success Endpoints

Per FDA Request, the following success endpoints will also be summarized in reports.

##### 3.3.1 FDA Device Success (at 1 month and all post-procedure follow-up visit intervals):

- Alive, with
- Original intended device in place, and
- No additional surgical or interventional procedures related to access or the device, and
- Intended performance of the device:
  - a) No migration, detachment, hemolysis, thrombosis or endocarditis and

Title

Statistical Analysis Plan for FORMA EFS

- b) Expected hemodynamic performance (i.e., TR reduction of one grade and TV gradient  $\leq$  5mmHg)
- c) No para-device complications (i.e., PPM, PE, SVC or subclavian thrombosis, damage to subvalvular apparatus of TV)

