5.1.3 OTHER ENDPOINTS

5.1.3.1 Echocardiographic parameters

- A. Reduction in TR severity (assessed by TR grade and quantitative measures) as assessed by TEE pre- and post-implant in the procedure room.

Additional echocardiographic parameters will be compared to baseline:

- B. TTE parameters assessed at baseline, discharge, 30 days, 6 months, 1 year and annually until 3 years post procedure.
1. TR grade- qualitative assessment
 2. Vena Contracta (2D)
 3. EROA (PISA/2D or 3D/3D color doppler)
 4. Regurgitant volume
 5. Tricuspid annular diameter (end-diastolic – S-L)
 6. Tricuspid annular area (2D/3D mid-diastolic)
 7. Tenting area and distance
 8. Forward stroke volume
 9. RV dimensions
 10. Right atria volume
 11. Left ventricular Ejection Fraction
 12. Inferior Vena Cava dimensions/respiratory variations
 13. Hepatic vein flow reversal
 14. Pulmonary artery pressure (peak)
 15. Right ventricular function

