**3.4 Other Endpoint: Echocardiographic parameters**

A. Reduction in TR severity (assessed by TR grade and quantitative measures) as assessed by TEE pre- and post-implant in the procedure room.

Additional echocardiographic parameters will be compared to baseline:

B. TTE parameters assessed at baseline, discharge, 30 days, 6 months, 1 year and annually until 3 years post procedure.

Revision Date: April 1, 2019

Rev

3.0

For Use Only by  
Affiliates of Edwards  
Lifesciences

Page 11 of 18

Title

Statistical Analysis Plan for FORMA EFS

1. TR grade- qualitative assessment
2. Vena Contracta (2D)
3. EROA (PISA/2D or 3D/3D color doppler)
4. Regurgitant volume
5. Tricuspid annular diameter (end-diastolic – S-L)
6. Tricuspid annular area (2D/3D mid-diastolic)
7. Tenting area and distance
8. Forward stroke volume
9. RV dimensions
10. Right atria volume
11. Left ventricular Ejection Fraction
12. Inferior Vena Cava dimensions/respiratory variations
13. Hepatic vein flow reversal
14. Pulmonary artery pressure (peak)
15. Right ventricular function

Final

 Edwards	Revision Date: April 1, 2019		Rev	3.0	For Use Only by Affiliates of Edwards Lifesciences	Page 12 of 18
	Title	Statistical Analysis Plan for FORMA EFS				

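### FDA Device Success does not count a device fracture as a failure, and the tricuspid gradient it requires is on neither TTE parameter list

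*SAP*

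**What the plan says.** SAP 3.3.1 defines FDA Device Success at 1 month and at every later visit. By SAP 5.2 that is five visits: 1 month, 6 months, and 1, 2 and 3 years. The patient must be alive and meet these further conditions:

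- "Original intended device in place, and"
- "No additional surgical or interventional procedures related to access or the device, and"
- (a) "No migration, detachment, hemolysis, thrombosis or endocarditis"
- (b) "Expected hemodynamic performance (i.e., TR reduction of one grade and TV gradient" of at most 5 mmHg
- (c) none of a short list of para-device complications.

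FDA Procedural Success (SAP 3.3.2, at 1 month) and FDA Individual Patient Success (SAP 3.3.3, at 6 months and 1 year) each start from Device Success and add conditions.

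Protocol 18 defines Device Fracture as "Break or other structural defect in anchor, railing, or spacer with or without embolization". It has separate entries for anchor detachment, anchor migration and spacer migration. Protocol 3.1 lists fracture among the device risks, and Protocol 12.1.6 requires suspected fractures to be entered on the eCRF.

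For echo, SAP 3.4 and Protocol 5.1.3.1 carry the same 15-item list under "TTE parameters assessed at baseline, discharge, 30 days, 6 months, 1 year and annually until 3 years post procedure".

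**The concern.** An endpoint that claims to measure intended performance should have a clear answer for a broken implant. Under SAP 3.3.1 the answer depends on what else happens to the patient. A fracture with no other consequence at the visit counts as success, and the two endpoints built on Device Success inherit that classification. For an early feasibility study meant to guide further device development, this is an event the summary should not absorb.

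The gradient raises a different problem. Inflow obstruction is a plausible failure for a spacer sitting in the valve orifice. Protocol 3.1 lists transvalvular flow disturbance and leaflet stenosis as risks. The SAP makes the gradient a condition of success, yet the parameter lists that say what the echo analysis will contain do not include it.

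**Working it through.** The plan gives no expected FDA success rate, fracture rate or missing-data rate, and the 60 patients have no statistical justification (SAP 2.3). There is no stated figure to reproduce. The check compares the texts and then works out what one patient is worth.

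**1. Which components would catch a fracture?**

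| Component of SAP 3.3.1 | Does a fracture fail it? |
|---|---|
| Alive | Only if the patient dies |
| Original device in place | Only if the device is no longer in place |
| No further procedure | Only if one follows |
| (a) five named events | Only if one of them also occurs; fracture is 0 of 5 |
| (b) TR reduction and gradient | Only if TR reduction is lost or the gradient rises above 5 mmHg |
| (c) para-device complications | Only if one also occurs |

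No row fails because of the fracture itself. The protocol's definition covers a break without embolization, so a fractured device that is still in place is a case it foresees.

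**2. Size of the fracture gap.** Let *k* be the number of fractures that trip no other component and *n* the denominator. Then the rate as written minus the rate with fracture as a failure is 100 × *k*/*n* points.

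- *n* = 60 (all patients): 100 × 1/60 = 1.67 points per fracture.
- *n* = 30 (one revision subgroup, SAP 4 and 8.4.4): 100 × 1/30 = 3.33 points per fracture.
- *k* = 0: no effect.

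Illustration, assuming that 40 of 60 patients succeed as the endpoint is written: 66.7% (95% Clopper-Pearson interval 53.3 to 78.3). With *k* = 1, 2, 3 or 5 the rate becomes 39/60 = 65.0%, 38/60 = 63.3%, 37/60 = 61.7% or 35/60 = 58.3%.

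SAP 8.3 names no analysis population, so *n* = 60 is itself an assumption. A smaller *n* makes each fracture count for more.

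**3. Is the gradient listed?** None of the 15 items in either list is a tricuspid gradient; the only pressure item is "Pulmonary artery pressure (peak". The follow-up table in Protocol 8.7 refers only to TTE measurements, tricuspid regurgitation and heart function. SAP 8.4.1 adds no gradient.

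**4. What would a missing gradient do?** Assume again that 40 of 60 patients meet every other component, and that 10 gradients are missing.

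- All 10 among the 40, excluded from the denominator: 30/50 = 60.0%.
- The same 10 treated as failures: 30/60 = 50.0%. Treated as passes: 40/60 = 66.7%. The true rate, if all other gradients pass, lies between these two.
- All 10 instead among the 20 who fail something else, and dropped for incomplete data: 40/50 = 80.0%, although all 10 are failures whatever their gradient and the true rate is 40/60 = 66.7%.

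So exclusion can move the rate either way.

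**5. Which rates are affected?** Device Success at five visits, Procedural Success at one and Individual Patient Success at two: 5 + 1 + 2 = 8. This reads Device Success in 3.3.2 and 3.3.3 as the FDA version in 3.3.1. For the last three rates the fracture effect is at most *k*/*n*, because a patient must also meet their added conditions.

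**The case against.** The strongest reply on fracture is that most clinically important fractures would fail the endpoint anyway, through loss of position, a further procedure, detachment, migration or loss of TR reduction. On this view, whether a break that leaves position and function intact is a failure is a matter of definition, in an endpoint included at FDA's request. Fractures are still recorded on the eCRF. That limits the size of the problem, possibly to zero. It does not remove the gap: the rule as written classes a defined structural failure as intended performance.

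On the gradient, the reply is that the 15 items are endpoints to be compared with baseline and do not limit what is acquired. Follow-up TTE is comprehensive and follows a core-lab acquisition protocol that is not part of these documents. The follow-up data list is expressly open-ended (Protocol 8.7), hemodynamic data are planned at the same visits (Protocol 13.3), and a core laboratory supplies the echo data (SAP 8.4.1). This stands. A reader might infer that the endpoint cannot be computed, but the documents do not show that. They show only that the plan does not secure the measurement.

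A reader might also infer that a patient without a gradient passes by default. SAP 6.1 and 6.2 say otherwise: patients with missing data leave the denominator and nothing is imputed. SAP 8.3 reports each component, and SAP 6.1 calls for numbers of observations, so missing gradients should be at least partly visible.

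Finally, these are descriptive summaries outside the protocol's safety and performance endpoints. No sample size or error rate depends on them.

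**Conclusion.** The fracture gap holds. SAP 3.3.1(a) omits an event that the protocol defines, anticipates and records, so a fracture with no other consequence at the visit scores as success. Each one adds 1.7 points at 60 patients or 3.3 points at 30. It would be going too far to say that the reported rates will be too high: that needs at least one fracture that trips no other component, and the documents give no fracture rate.

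The gradient point holds as a mismatch between the endpoint and the listed measurements. How many gradients will be missing is unknown, and so is the direction of any effect. The figures in the illustrations rest on an assumed 40 of 60 and an assumed 10 missing.

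Eight rates are touched. It would be wrong to count three endpoints at five visits each, because Procedural Success is assessed once and Individual Patient Success twice. The change is worth making because the fracture data are already collected and the correction costs little.

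**What to change.** - In SAP 3.3.1(a), add *fracture*, as defined in Protocol 18, to the listed failures. If the FDA wording has to stay, report the rate with and without fracture side by side.
- In Protocol 5.1.3.1 and SAP 3.4, add TV gradient for the follow-up visits, specified as mean or peak to match the core-lab acquisition protocol and read from the TTEs already scheduled. At each visit, report the number of patients without a gradient.
- Optional tidying: write *at least one grade* in (b), so that a larger reduction plainly qualifies. Write *new* before PPM and PE in (c), since patients with one lead or a non-significant effusion can be enrolled.

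The cost is wording in both documents, possibly one more core-lab reading on existing images, and a success rate that may come out slightly lower.
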